7.4 ECOG Performance Status

The performance status will be scored using the ECOG Performance Status Scale (Oken, 1982), as described in [Table 7-3](#).

ECOG Performance Status will be assessed and recorded at screening, on Day 1, and at each follow-up visit. Assessment of ECOG Performance Status should be performed on the scheduled day, even if study medication is being held. Time to deterioration of ECOG performance status, from baseline will be assessed

Table 7-3 ECOG Performance Status

Score	Performance status
0	Fully active, able to carry on all pre-disease performance without restriction
1	Restricted in physically strenuous activity but ambulatory and able to carry out work of a light or sedentary nature, e.g., light housework, office work
2	Ambulatory and capable of all self-care but unable to carry out any work activities. Up and about more than 50% of waking hours
3	Capable of only limited self-care, confined to bed or chair more than 50% of waking hours
4	Completely disabled. Cannot carry on any self-care. Totally confined to bed or chair
5	Dead

8 Safety monitoring and reporting

8.1 Adverse events

8.1.1 Definitions and reporting

An adverse event is defined as the appearance of (or worsening of any pre-existing) undesirable sign(s), symptom(s), or medical condition(s), that occur after patient's signed informed consent has been obtained.

Abnormal laboratory values or test results occurring after informed consent constitute adverse events only if they induce clinical signs or symptoms, are considered clinically significant, require therapy (e.g. hematologic abnormality that requires transfusion or hematological stem cell support), or require changes in study drug(s).

Except for screening failures, Adverse events that begin or worsen after informed consent should be recorded in the Adverse Events CRF. Conditions that were already present at the time of informed consent should be recorded in the Medical History/Current Medical Conditions CRF. Adverse event monitoring should be continued for at least 30 days (\pm 2 days) following the last dose of everolimus. Adverse events (including laboratory abnormalities that constitute AEs) should be described using a diagnosis whenever possible, rather than individual underlying signs and symptoms. When a clear diagnosis cannot be identified, each sign or symptom should be reported as a separate Adverse Event.

Adverse events will be assessed according to the Common Terminology Criteria for Adverse Events (CTCAE) version 4.03. If CTCAE grading does not exist for an adverse event, the severity of mild, moderate, severe, and life-threatening, corresponding to Grades 1 - 4, will be used. CTCAE Grade 5 (death) will not be used in this study; rather, information about deaths will be collected through a Death form.

The occurrence of adverse events should be sought by non-directive questioning of the patient (subject) during the screening process after signing informed consent and at each visit during the study. Adverse events also may be detected when they are volunteered by the patient during the screening process or between visits, or through physical examination, laboratory test, or other assessments.

Progression of malignancy (including fatal outcomes), if documented by use of RECIST (version 1.1) will not be reported as a serious adverse event. Adverse events separate from the progression of malignancy (example, deep vein thrombosis at the time of progression or hemoptysis concurrent with finding of disease progression) will be reported as per usual guidelines used for such events with proper attribution regarding relatedness to the study drugs.

As far as possible, each adverse event should be evaluated to determine:

1. The severity grade (CTCAE Grade 1-4)
2. Its duration (Start and end dates or Ongoing at End of Study)
3. Its relationship to the study treatment (Reasonable possibility that AE is related: No, Yes)
4. Action taken with respect to study or investigational treatment (none, dose adjusted, temporarily interrupted, permanently discontinued, unknown, not applicable)
5. Whether medication or therapy was given (no concomitant medication/non-drug therapy, concomitant medication/non-drug therapy)
6. Whether it is serious, where a serious adverse event (SAE) is defined as in [Section 8.2.1](#)

All adverse events should be treated appropriately. If a concomitant medication or non-drug therapy is given, this action should be recorded on the Adverse Event CRF.

Once an adverse event is detected, it should be followed until its resolution or until it is judged to be permanent, and assessment should be made at each visit (or more frequently, if necessary) of any changes in severity, the suspected relationship to the study treatment, the interventions required to treat it, and the outcome.

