7.2.1 Physical examination, height and weight

Physical examination must comprise a total body examination (general appearance, skin, neck, including thyroid, eyes, ears, nose, throat, lungs, heart, abdomen, back, lymph nodes and extremities).

Physical examination will be performed at screening, on treatment Day 1 (prior to administration of the study drug, unless physical examination in screening was done less than 7 days before Day 1), as well as at Week 4, Week 10, Week 20, Week 30, Week 40, and Week 50 or End of treatment visit.

Information for all physical examinations must be included in the source documentation at the study site. Significant findings that are present prior to the start of study drug must be documented on the Medical History / Current medical Conditions CRF. Significant findings made after the start of study drug, which meet the definition of an adverse event, must be recorded on the Adverse Event CRF.

Height and weight will be measured at the screening visit.

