7.2.2 Vital signs

Vital signs will be recorded on the appropriate CRF pages at each visit. Heart rate and blood pressure will be measured according to normal medical practice.

The particular clinical findings seen before taking study drug must be documented in the Relevant Medical History CRF. The findings that are compatible with adverse events after taking study drug must be documented in the Adverse Event CRF.

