7.2.3 Laboratory evaluations

Laboratory evaluations should be performed locally at every protocol required visit ([Table 7-1](#)) or as frequently as clinically indicated. The patient should be in a fasting state for 12 hours at the time of blood sampling.

All scheduled laboratory evaluations must be obtained according to the specified visit window in [Table 7.1](#), whether or not study treatment is administered. Screening examinations performed ≤ 7 days of the first dose of study treatment do not need to be repeated on Day 1.

Laboratory values will be recorded in the patient's source documents and must not be documented in the CRF. However, any particular clinically significant findings seen before taking study drugs must be documented in the Relevant Medical History/Current Medical Conditions CRF.

Abnormal laboratory parameters that are considered clinically significant, induce clinical signs or symptoms, require concomitant therapy (e.g. hematologic abnormality that requires transfusion or hematological stem cell support), or require changes in study treatment, or require changes in study drug(s) constitute adverse events in their own right and must be recorded on the Adverse Events CRF.

Whenever possible, a diagnosis, rather than a symptom should be provided (e.g. anemia instead of low hemoglobin). Laboratory abnormalities that meet the criteria for Adverse Events should be followed until they have returned to normal or an adequate explanation of the abnormality is found. When an abnormal laboratory or test result corresponds to a sign/symptom of an already reported adverse event, it is not necessary to separately record the lab/test result as an additional event.

Laboratory abnormalities, that do not meet the definition of an adverse event, should not be reported as adverse events. A Grade 3 or 4 AE (severe) as per CTCAE does not automatically indicate a SAE unless it meets the definition of serious as defined below and/or as per investigator's discretion. A dose hold or medication for the lab abnormality may be required by the protocol and is still, by definition, an adverse event.

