8.2.2 Reporting

Every SAE, regardless of suspected causality, occurring after the patient has provided informed consent and until 30 days after the patient has stopped study treatment/participation must be reported to Novartis within 24 hours of learning of its occurrence.

Any SAE experienced after this 30-day period should only be reported to Novartis if the investigator suspects a causal relationship to the study drug.

Recurrent episodes, complications, or progression of the initial SAE must be reported as follow-up to the original episode within 24 hours of the investigator receiving the follow-up information. An SAE occurring at a different time interval or otherwise considered completely unrelated to a previously reported one should be reported separately as a new event.

Information about all SAEs is collected and recorded on the Serious Adverse Event Report Form; all applicable sections of the form must be completed in order to provide a clinically thorough report. The investigator must assess and record the relationship of each SAE to each specific study drug, complete the SAE Report Form in English, and send the completed, signed form by fax within 24 hours to the oncology Novartis Drug Safety and Epidemiology (DS&E) department.

The telephone and telefax number of the contact persons in the local department of Drug Safety and Epidemiology (DS&E), specific to the site, are listed in the investigator folder provided to each site. The original copy of the SAE Report Form and the fax confirmation sheet must be kept with the case report form documentation at the study site.

Follow-up information is sent to the same contact(s) to whom the original SAE Report Form was sent, using a new SAE Report Form stating that this is a follow-up to the previously reported SAE and giving the date of the original report. Each re-occurrence, complication, or progression of the original event should be reported as a follow-up to that event regardless of when it occurs. The follow-up information should describe whether the event has resolved or continues, if and how it was treated, and whether the patient continued the study or withdrew from study participation.

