Changes in patient's condition (investigator's discretion)	xx (xx.x)	NA	xx (xx.x)	NA	xx (xx.x)	NA

	Asian (N=xx)		Non-Asian (N=xx)		Total (N=xxx)	
	Everolimus (N=xxx)	Exemestane (N=xxx)	Everolimus (N=xxx)	Exemestane (N=xxx)	Everolimus (N=xxx)	Exemestane (N=xxx)
Need for other types of anticancer therapy (excluding palliative radiation for bone lesions)	xx (xx.x)	NA	xx (xx.x)	NA	xx (xx.x)	NA
Everolimus dose interruption > 4 wks	xx (xx.x)	NA	xx (xx.x)	NA	xx (xx.x)	NA
Other	xx (xx.x)	NA	xx (xx.x)	NA	xx (xx.x)	NA

NA: Not applicable SD: Standard deviation.

Asian: Indonesia, India, Vietnam, Turkey, South Korea, Thailand, Malaysia, Taiwan or Jordan.

Non-Asian: Australia, Morocco, South Africa or Tunisia.

^a Days with a zero dose level due are to temporary interruptions caused by safety reasons or patients' non-compliance.

^b Study treatment discontinuation refers to a patient's withdrawal from everolimus.

Table 6.1 Summary Overview of All Treatment-Emergent Adverse Events Summary, Any CTCAE Grade Overall and in Asian Subgroup - Safety Set

Adverse Event	Asian (N=xx)	Non-Asian (N=xx)	Total (N=xxx)
Number of patients, n (%)			
With no TEAE	xx (xx.x)	xx (xx.x)	xx (xx.x)
With at least one TEAE	xx (xx.x)	xx (xx.x)	xx (xx.x)
With at least one drug-related TEAE ^a	xx (xx.x)	xx (xx.x)	xx (xx.x)
With at least one serious TEAE	xx (xx.x)	xx (xx.x)	xx (xx.x)
TEAE leading to death	xx (xx.x)	xx (xx.x)	xx (xx.x)
Non-fatal serious TEAE	xx (xx.x)	xx (xx.x)	xx (xx.x)
With at least one serious drug-related TEAE, n (%)	xx (xx.x)	xx (xx.x)	xx (xx.x)
AE leading to death	xx (xx.x)	xx (xx.x)	xx (xx.x)
Non-fatal serious TEAE	xx (xx.x)	xx (xx.x)	xx (xx.x)
TEAE leading to treatment discontinuation, n (%)	xx (xx.x)	xx (xx.x)	xx (xx.x)
With at least one treatment-emergent AESI, n (%)	xx (xx.x)	xx (xx.x)	xx (xx.x)

Asian: Indonesia, India, Vietnam, Turkey, South Korea, Thailand, Malaysia, Taiwan or Jordan.

Non-Asian: Australia, Morocco, South Africa or Tunisia.

TEAE: Treatment emergent adverse event. TEAE are defined as any adverse event with a start date on or after the date of the first dose of study drug and within 30 days of treatment discontinuation. AESI = Adverse events of special interest.

Adverse events are coded using MedDRA version 19.1. AEs are assessed using CTCAE version 4.03.

Percentages are based on the number of patients in the Safety Set.

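### Two cut-points, consent and first dose, decide whether a screening-period finding is Medical History or an AE, and under the SAP's start-date rule its on-treatment worsening can be lost from the primary safety tables

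*Protocol*

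**What the plan says.** **Cut at consent.** Protocol 8.1.1 defines an AE as "the appearance of (or worsening of any pre-existing) undesirable sign(s), symptom(s), or medical condition(s), that occur after patient's signed informed consent". It then gives two recording rules: "Except for screening failures, Adverse events that begin or worsen after informed consent should be recorded in the Adverse Events CRF", and "Conditions that were already present at the time of informed consent should be recorded in the Medical History/Current Medical Conditions CRF".

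**Cut at first dose.** The assessment sections use a different moment.
- 7.2.1, physical examination: "Significant findings that are present prior to the start of study drug must be documented on the Medical History".
- 7.2.2, vital signs: "The particular clinical findings seen before taking study drug must be documented in the Relevant Medical History CRF".
- 7.2.3, laboratory: "any particular clinically significant findings seen before taking study drugs must be documented in the Relevant Medical History/Current Medical Conditions CRF".
- 7.2.3.6 does the same for ECG findings that predate treatment.
- 7.1.1 directs screening laboratory results that are out of range and clinically significant to the Medical History CRF.

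Section 7.2.3 also contains a rule with no time limit, repeated in 8.1.2.1, that clinically significant laboratory abnormalities go on the AE CRF.

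**Analysis.** Protocol 10.5 summarises treatment-emergent AEs and includes events that have worsened relative to baseline. The footnote to SAP Table 6.1, repeated under the later AE tables, defines a treatment-emergent AE as "any adverse event with a start date on or after the date of the first dose of study drug", up to 30 days after discontinuation. It has no worsening criterion.

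**The concern.** Consent precedes every study-specific screening procedure, and first dose may follow by up to 21 days. Table 7-1 collects AEs at screening and Day 1. Laboratory tests more than 7 days old are repeated on Day 1, and the physical examination is repeated unless it was done less than 7 days earlier. Changes inside the window will therefore be seen, and each change of the listed types has two prescribed destinations. For a clinically significant laboratory value, both destinations are stated within 7.2.3 itself.

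Safety is the primary objective, and its laboratory component consists of changes that qualify as AEs. If two sites can record the same clinical course differently, and one version is counted while the other is not, the incidence by term and grade depends partly on which section the site followed. The baseline medical-history summary (SAP Table 2.5) moves with the same choice.

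**Working it through.** The plan gives no figure to reproduce: the study is descriptive and the sample is one of convenience. The check is to follow one finding, with onset after consent and before first dose, through each recording route and then through each definition of treatment emergence.

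| Case | Course on treatment | How recorded | Protocol 10.5 | SAP rule |
|---|---|---|---|---|
| a1 | Unchanged | Medical History | Not counted | Not counted |
| a2 | Unchanged | AE CRF, pre-dose start date | Not counted | Not counted |
| b | Worsens | Medical History first; the worsening is a new AE with an on-treatment start date | Counted | Counted |
| c | Worsens | AE CRF, one record, grade updated | Counted as worsening | **Not counted** |
| d | Worsens | AE CRF, new record at the grade change | Counted | Counted |

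Cases a1 and a2 agree, so routing has no effect on the treatment-emergent tables for a finding that does not change. Cases b and c are the same clinical course with different SAP results. Case d shows that the loss disappears if a grade change opens a new record.

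The documents do not settle whether c or d applies. Protocol 8.1.1 asks for changes in severity to be assessed at each visit, but does not say that a change starts a new entry. The AE listings among the SAP shells (14.1 to 14.3) cover treatment-emergent events, so a case c event would not surface there either. CRF laboratory data are not a dependable check: protocol 7.1 and 7.2.3 keep laboratory values out of the CRF, while the SAP shells plan laboratory tables without making the data source clear.

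The number of patients affected is a product:

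N × (share with a screening-onset finding that worsens on treatment) × (share of those kept in one AE record)

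Only N, up to 400, is in the documents. As an assumption for scale, let the first share be 1% to 5%: 400 × 0.01 = 4 and 400 × 0.05 = 20 patients. The last share is unknown and can lie anywhere from 0 to 1, so the number lost would lie between 0 and 20 under that assumption.

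**The case against.** The case for leaving this as a minor wording point is substantial.

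- **A reader might infer that all screening-period events move in and out of the primary endpoint by site.** They do not. Cases a1 and a2 show that both definitions exclude pre-dose onset without later change.
- **A reader might infer that everything seen before first dose goes to Medical History.** The sections cover significant examination, vital-sign, laboratory and ECG findings. Symptoms elicited by questioning after consent remain AEs under 8.1.1, and 7.2 does not forbid an additional AE entry.
- **A reader might infer that a serious pre-dose event escapes reporting.** Section 8.2.2 covers "Every SAE, regardless of suspected causality, occurring after the patient has provided informed consent", on a separate form within 24 hours, and nothing in 7.2 displaces that.
- **The BOLERO-2 rates in Table 1-1 (anaemia 21%, hyperglycaemia 14%) might seem to give a size.** They are incidences during that trial's treatment, not onset rates in a pre-dose window.
- **The loss arises in the SAP definition, and the shells lean towards separate records.** Listing 14.1 has one grade and one start date per row, and the Table 6.2.1 footnote places one AE with several grades in several grade columns.
- **A consent cut-point is hard to apply** to an abnormality first found at the first test after consent.

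The first four limits stand in full. The fifth is partly right: the shells suggest case d but do not establish it, and CRF completion guidelines are not among the documents. Correcting the SAP alone would still leave two CRF cut-points and the shift in Table 2.5. It would also need a dated grade change to work from, which a single updated record may not supply. The last objection is answered by a convention in the fix.

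**Conclusion.** The recording rules contradict each other for significant examination, vital-sign, laboratory and ECG findings with onset between consent and first dose. The effect on the primary safety tables is confined to patients whose screening-onset finding worsens on treatment and is kept in its original AE record. For them the SAP rule drops an event that protocol 10.5 would count, and the loss falls on sites that followed 8.1.1. Baseline medical history shifts with routing whether or not the finding later worsens.

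The documents give no frequency. The 0 to 20 patients shown rests on an unanchored assumption of 1% to 5% and on an unknown share kept in one record; it may be close to zero if sites open new records. No hypothesis test, power or sample-size figure is involved. The point is worth correcting because the inconsistency affects how a primary endpoint is captured and the correction is cheap.

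**What to change.** 1. Use the 8.1.1 consent cut-point in 7.1.1, 7.2.1, 7.2.2, 7.2.3 and 7.2.3.6. A finding present at consent goes to Medical History; one that first appears or worsens after consent, and meets the AE definition, goes on the AE CRF.
2. State a convention for unknown onset: an abnormality found at the first assessment after consent, with no evidence of later onset, is treated as present at consent.
3. State in 8.1.1 and in the CRF guidance that any on-treatment increase in grade is entered as a new AE record with its own start date.
4. Add worsening on or after first dose to the treatment-emergent definition in the SAP footnotes, so that it matches protocol 10.5.

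The cost is wording in the protocol and SAP plus CRF completion guidance. No new assessment or data collection is needed.

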8.1.2 Laboratory test abnormalities

8.1.2.1 Definitions and reporting

Laboratory abnormalities that constitute an Adverse event in their own right (are considered clinically significant, induce clinical signs or symptoms, require concomitant therapy or require changes in study treatment), should be recorded on the Adverse Events CRF. Whenever possible, a diagnosis, rather than a symptom should be provided (e.g. anemia instead of low hemoglobin). Laboratory abnormalities that meet the criteria for Adverse Events should be followed until they have returned to normal or an adequate explanation of the abnormality is found. When an abnormal laboratory or test result corresponds to a sign/symptom of an already reported adverse event, it is not necessary to separately record the lab/test result as an additional event.

Laboratory abnormalities, that do not meet the definition of an adverse event, should not be reported as adverse events. A Grade 3 or 4 event (severe) as per CTCAE does not automatically indicate a SAE unless it meets the definition of serious as defined below and/or as per investigator's discretion. A dose hold or medication for the lab abnormality may be required by the protocol in which case the lab abnormality would still, by definition, be an adverse event and must be reported as such.

8.1.3 Adverse events of special interest

The adverse events of special interest associated with mTOR inhibition include:

- Stomatitis
- Non-infectious pneumonitis
- Infections
- Hyperglycemia
- Hyperlipidemia
- Hypophosphatemia
- Skin Rash
- Hypersensitivity
- Wound healing complications
- Increased creatinine/renal failure/proteinuria
- Cardiac failure

8.2 Serious adverse events

8.2.1 Definitions

A serious adverse event (SAE) is defined as one which:

- Is fatal or life-threatening
- Results in persistent or significant disability/incapacity
- Constitutes a congenital anomaly/birth defect
- Is medically significant, i.e., defined as an event that jeopardizes the patient or may require medical or surgical intervention to prevent one of the outcomes listed above
- Requires inpatient hospitalization or prolongation of existing hospitalization,
Note: hospitalizations for the following reasons should not be reported as serious adverse events:
 - Routine treatment or monitoring of the studied indication, not associated with any deterioration in condition, if any
 - Elective or pre-planned treatment for a pre-existing condition that is unrelated to the indication under study and has not worsened since signing the informed consent

- Social reasons and respite care in the absence of any deterioration in the patient's general condition
Note: treatment on an emergency outpatient basis that does not result in hospital admission and involves an event not fulfilling any of the definitions of a SAE given above is not a serious adverse event

